2.4.5.1.3 Sensitivity to handling of missing data

Sensitivity analyses will be conducted to assess the robustness of primary efficacy analysis with regards to handling of missing data (Section 2.5.3) (4). For all sensitivity analyses, outputs will be first described separately on the Type 1 diabetes patients and on the Type 2 diabetes patients, and then on the pooled data in ITT population. Forest plots will be also provided.

Multiple imputations:

In addition to the MMRM method, the multiple imputation method will be used to address missing values, in the randomized population, followed by the testing of treatment arms using an analysis of covariance (ANCOVA) model, with the intent to evaluate the robustness of the primary analysis using a different statistical method. Missing data from the randomized population will be imputed 100 times to generate 100 complete data sets, using the MI SAS procedure (using Markov Chain Monte Carlo). The percent change from baseline at Week 24 will be then derived from observed and imputed calculated LDL-C at this time point. The 100 complete data sets will be then analyzed using an ANCOVA model with treatment group and randomization strata (as per IVRS) as fixed effects, and the baseline calculated LDL-C value as continuous covariate, and the MIANALYZE procedure will be used to generate valid statistical inferences by combining results from the 100 analyses using Rubin's formulae (5, 6). The model for assessing the treatment effect by diabetes type will include an additional interaction: the treatment group-by-strata interaction.

The number of imputations (100) will be informally verified by replicating sets of 100 imputations and checking whether the combined results are stable. If not stable, the number of imputations will be increased and informally checked as above, and thus until stable estimates are obtained.

The imputation model will include:

- The variables included in the ANCOVA model, including the treatment group, the randomization strata (as per IVRS) and the baseline value. The model for assessing the treatment effect by diabetes type will include an additional interaction: the treatment group-by-strata interaction.
- The baseline characteristics such as: age, BMI, and gender. Age and BMI will be included as continuous variables.
- The calculated LDL-C values at Week 8, Week 12, Week 20 and Week 24 time points. Time points are those defined in Section 2.5.4.

Non continuous variables included in the imputer's model (ie, treatment group and gender) are not expected to be missing.

Pattern mixture model (see Appendix D for more details):

Multiple imputations will be used with different imputation strategies applied to calculated LDL-C values missing during the on-treatment period (ie, within the time period from the first double blind IMP injection up to the day of last injection +21 days) versus calculated LDL-C values missing after treatment discontinuation (ie, after the day of last injection +21 days) based on the following assumptions:

- Patients within 21 days of their last blind IMP injection would continue to show benefit from treatment similar to that observed at the scheduled time point. Therefore, calculated LDL-C values missing during the on-treatment period (eg., samples obtained out-side the specified window, no blood sample available although visit was performed, etc.) should be considered "Missing At Random" and imputed based on other on-treatment measurements.
- Patients who stopped taking their study treatment no longer benefited from it after discontinuation, and thus tended to have calculated LDL-C values returning to baseline. Therefore, calculated LDL-C values missing more than 21 days after treatment discontinuation should be imputed based on patient's own baseline value.

Missing calculated LDL-C values will be imputed 100 times to generate 100 complete data sets. The percent change from baseline to Week 24 will be derived from observed and imputed calculated LDL-C at this time point. The completed data sets will be analyzed using an ANCOVA model with treatment group and randomization strata (as per IVRS) as fixed effects, and the baseline calculated LDL-C value as continuous covariate. The model for assessing the treatment effect by diabetes type will include an additional interaction: the treatment group-by-strata interaction. The results from the 100 analyses will be combined using Rubin's formulae (6).

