2.4.5 Analyses of efficacy endpoints

For statistics where international and conventional units do not impact the results (eg, means and least square (LS) means for percent changes from baseline, p-values for both percent and absolute changes from baseline, rates of patients below a threshold), derivations will be done and statistical models will be run using conventional units. For other statistics (eg, descriptive statistics at baseline and over time, absolute changes from baseline), derivations will be done with both international and conventional units.

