2.4.5.2.3 Binary endpoints

Binary secondary efficacy endpoints defined in [Section 2.1.3.2](#) (eg, proportion of patients below a threshold) will be analyzed using logistic regression with treatment group as main effect and corresponding baseline value(s) as covariate, stratified by randomization strata. Missing values will be addressed using a multiple imputation approach (see [Section 2.4.5.1.3](#)). The variables in the multiple imputation model will at least include the same variables as used in the logistic regression model. In the logistic regression model, the analyzed endpoint at time point of interest will be derived from observed and imputed lipid values at this time point. Treatment effects will be compared and the combined odds ratio estimate between the treatment groups, with their

corresponding 95% CIs and p-value will be provided via the SAS MIANALYZE procedure. The analysis will be performed by diabetes type and on the pooled data.

In the data dependent case that the logistic regression method is not applicable (eg, the response rate is zero in 1 treatment arm and thus the maximum likelihood estimate may not exist), the last observation carried forward (LOCF) approach would be used for handling of missing values and an exact conditional logistic regression would be performed to compare treatment effects. The LOCF imputation method will consist of using the last value obtained up to the Week 24 analysis window (or Week 12 as applicable) to impute the missing week 24 value (or Week 12 respectively).

In case of computing issues with exact logistic regression, the baseline level(s) will be entered in the model as a categorical variable(s) using quartiles. Exact odds ratio versus placebo, 95% CI, and p-value will be provided.

2.4.5.2.4 *Summary of results per time point*

Central laboratory values (in conventional (US) and international units), percent change from baseline and/or when appropriate absolute change from baseline (in conventional and international units) in calculated LDL-C, measured LDL-C, HDL-C, fasting TG, non-HDL-C, TC, ratio TC/HDL-C, Lp(a), Apo B, Apo A-1, ratio Apo B/Apo A-1, Apo C-III, TGRL, LDL-C particle size, LDL-C particle number will be provided at each time point for each treatment group in the ITT population using:

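### The LDL-C imputation model in SAP 2.4.5.1.3 has no term letting baseline or earlier-visit slopes differ by arm, so the imputed treatment effect can be slightly biased, in either direction

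*SAP*

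**What the plan says.** SAP 2.4.5.1.3 adds an MI analysis "with the intent to evaluate the robustness of the primary analysis using a different statistical method". Missing calculated LDL-C is imputed 100 times by the MCMC method of the SAS MI procedure. The imputation model is to contain:

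- "The variables included in the ANCOVA model, including the treatment group, the randomization strata (as per IVRS) and the baseline value";
- baseline characteristics, with age, BMI and gender given as the examples;
- "The calculated LDL-C values at Week 8, Week 12, Week 20 and Week 24 time points".

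One interaction is named: "The model for assessing the treatment effect by diabetes type will include an additional interaction: the treatment group-by-strata interaction". The same subsection counts treatment group among the non-continuous variables of the imputer's model, so treatment is a covariate and not a grouping for separate runs.

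SAP 2.4.5 says that, for percent change, "derivations will be done and statistical models will be run using conventional units", so the imputed quantity is in mg/dL. After imputation, "The percent change from baseline at Week 24 will be then derived from observed and imputed calculated LDL-C at this time point", and the result goes into an ANCOVA with treatment, stratum and baseline.

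Other sections rely on this model. SAP 2.4.5.2.3 says "Missing values will be addressed using a multiple imputation approach" for the binary endpoints and points back to 2.4.5.1.3. SAP 2.4.5.2.2 does the same for TG, TGRL and Lp(a). SAP 2.4.5.1.2 examines treatment-by-baseline heterogeneity, but only in the MMRM.

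**The concern.** A joint normal model with treatment as one more variable gives both arms the same regression of Week 24 LDL-C on baseline and on earlier visits. The treatment effect it imputes at a given history is therefore a fixed gap in mg/dL. The ANCOVA that follows has one treatment term for percent change, which is a fixed gap in percent. The two agree only in special cases.

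There are two reasons to expect the slopes to differ by arm. If the drug lowers LDL-C roughly in proportion, the mg/dL slope on baseline is near 1 on placebo and near 0.5 on alirocumab. And the dose rule (Protocol 6.1, SAP 1.4) up-titrates at Week 12 only those alirocumab patients whose Week 8 LDL-C is 70 mg/dL or more, which changes the Week 8 to Week 24 relation in one arm only.

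What is at stake is how the robustness check is read. If MMRM and MI disagreed, one could not tell sensitivity to missing data from misfit of the imputation model.

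**Working it through.** The plan gives no figure on this point, and its sample-size section is redacted, so there is nothing to reproduce first.

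**Inputs from the documents.** Protocol 4 reports prior Week 24 changes of -45.6% to -48.9% on the up-titration regimen and +0.5% to +4.2% on placebo. I take -47.5% and +2%, a difference of -49.5 points. SAP 1.1 gives 333 and 167 patients.

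**Assumed inputs.** Lognormal baseline with mean 110 mg/dL and realised CV 0.23 to 0.45; SD of percent change 25 points; between-visit correlation 0.6; about 10% missing at Week 24.

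**1. Effect implied at a given baseline, no post-baseline value.** Under a proportional effect the slopes on baseline are 1.02 (placebo) and 0.525 (alirocumab). A common-slope model replaces the gap 0.495 × B by 0.495 × 110 = 54.45 mg/dL at every baseline. The implied percent effect is 54.45/B:

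- B = 70: 77.8%
- B = 110: 49.5%
- B = 160: 34.0%

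**2. Average over imputed patients.** The bias is 49.5 × (mean(B) × average of 1/B among the imputed − 1). If missingness is unrelated to a lognormal baseline, the product is 1 + CV². At CV 0.33 the effect is too large by 49.5 × 0.109 = 5.4 points. If the imputed patients have high baselines, 1/B is small and the sign changes.

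**3. With an earlier visit seen.** The error shrinks by about 1 − 0.6 = 0.4. At B = 70 the implied effect is 49.5 × [1 + 0.4 × (110/70 − 1)] = 60.8%; at B = 160 it is 43.3%.

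**4. Large-sample simulation, proportional effect, no up-titration** (N = 1,000,000 per setting). Bias in percentage points; negative means too large an effect.

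| Missingness | Imputed, no post-baseline value | Imputed, Weeks 8, 12, 20 seen | Whole trial |
|---|---|---|---|
| Unrelated to baseline | -2.4 to -10.3 | -0.5 to -1.6 | -0.05 to -1.0 |
| Commoner at low baseline | -8.4 to -22.0 | -1.7 to -4.2 | -0.2 to -2.0 |
| Commoner at high baseline | +4.1 to +5.7 | +0.8 to +1.4 | +0.1 to +0.6 |

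The whole-trial extremes suppose that every missing patient follows one pattern (for example, 10% × 10.3 = 1.0). With an effect constant in mg/dL there was no bias beyond simulation noise. Adding treatment-by-baseline cut the whole-trial bias under a proportional effect to 0.06 points or less.

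**5. Adding up-titration** (N = 600,000; CV 33%; missingness unrelated to baseline). Effect among imputed patients, in points:

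| Setting | True | SAP model: no post-baseline / Week 8 seen / Weeks 8, 12, 20 seen | Imputed by arm |
|---|---|---|---|
| Proportional, further 20% on titration | -49.9 | -56.0 / -53.8 / -51.8 | -49.6 to -49.8 |
| Constant mg/dL, further 15 mg/dL on titration | -50.8 | -53.0 / -52.6 / -51.6 | -50.5 to -51.1 |

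So the one-sided titration rule alone brings some bias back.

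**6. Size in the trial.** Take -47% against +3% with up-titration, and 10% missing unrelated to baseline, of which 3% have no post-baseline value. Imputed patients then show -54.8 against a true -50.8, so the whole-trial shift is 0.10 × 4.0 = 0.4 points. It is 0.2 to 0.6 over 5% to 15% missing, and 0.2 with no titration effect. Patients with no post-baseline value (-58.3 against -50.4) supply 0.03 × 7.9 = 0.24 of the 0.4.

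In 1,200 simulated trials of 333/167 (sequential normal regression under monotone dropout, 10 imputations) the mean shift from complete data was -0.35 points with the SAP model and +0.01 by arm. The SD of the estimate was 2.50 and 2.47.

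**The case against.** The strongest reply is that this is too small to matter. A shift of 0.35 points is 0.35/2.50 = 0.14 of the SD of the estimate, on an effect near 50. It sits in a sensitivity analysis, and the primary MMRM models percent change directly. The SAP also has a pattern-mixture analysis and the treatment-by-baseline check in the MMRM. All of that stands, and it limits the point to a cheap improvement.

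The largest figures come from patients with no post-baseline LDL-C. They are outside the ITT population, and 2.4.5.1.3 is unclear about them: it imputes in the randomized population but says outputs are for ITT. Without them, 7% missing with a bias of 0.5 to 4.0 points gives 0.04 to 0.28 points (step 4 settings, no up-titration).

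The list of terms is not said to be exhaustive. The baseline characteristics are examples, and 2.4.5.2.2 and 2.4.5.2.3 set only a minimum. Nothing forbids arm-specific slopes; the plan simply does not provide them.

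A reader might infer that the bias always favours alirocumab. The documents do not support that: they do not establish a proportional effect (the 40 to 90 mg/dL range of absolute reductions in Protocol 4 is across studies, not a slope on baseline), nor who will be missing, and the sign depends on both.

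A reader might also infer that the target-attainment, TG or Lp(a) results are tilted toward the drug. That is not shown. In the step 6 simulation the imputed share below 70 mg/dL was 71.5% against a true 78.1% on alirocumab and 10.5% against 15.8% on placebo. The difference is 61.0 points against a true 62.3, slightly against the drug. Imputing by arm gave 75.9% and 16.3%: each share is closer, but their difference (59.6) is not. The target-attainment key secondaries also use the on-treatment population, which excludes patients with no post-baseline value. TG and Lp(a) were not simulated.

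**Conclusion.** The point holds as a modest specification gap. The imputation model works in mg/dL with slopes common to both arms, while the analysis is of percent change and the titration rule acts in one arm only. The imputed effect can be too large (missingness unrelated to baseline, or commoner at low baseline) or too small (commoner at high baseline). It is essentially unbiased if the effect is constant in mg/dL with no titration effect.

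With baseline mean 110 mg/dL, CV about 33% and roughly 10% missing unrelated to baseline, the whole-trial shift is a few tenths of a point on an effect near 50, mostly from patients with no or few post-baseline values. It grows roughly in proportion to the missing fraction. None of these inputs is in the documents. The superiority conclusion and the primary MMRM are not at risk; what suffers is the meaning of any difference between MMRM and MI.

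**What to change.** In SAP 2.4.5.1.3, state that the imputation is run separately by treatment group, with stratum, baseline, age, BMI, gender and the Week 8 to 24 LDL-C values in each run. Adding treatment-by-baseline and treatment-by-earlier-visit terms to a single model is an acceptable alternative. Keeping stratum within each arm already covers the treatment-by-strata term needed for the by-type analysis.

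Apply the same rule where 2.4.5.2.2 and 2.4.5.2.3 refer back to this model. The reason there is consistency, not a demonstrated tilt.

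The cost is a sentence of SAP text and a BY statement. The downside is a few more parameters to estimate in the placebo arm, which has about 167 patients in the pooled data; the trial-level simulation showed no loss of precision.

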2.4.5.1.4 Subgroup analyses

To assess the homogeneity of the treatment effect across various subgroups, treatment-by-subgroup factor, time point-by-subgroup factor and treatment-by time point-by subgroup factor interaction terms and a subgroup factor term will be added as fixed factors in the primary MMRM model for the pooled data described in [Section 2.4.5.1.1](#). For assessing the treatment effect by diabetes type, the same model will be fitted within each stratum, therefore without the strata factor and the interactions of strata with other factors. In case of non-convergence of the model, a model with less interaction coefficients will be fitted.

As for the primary efficacy analysis, all outputs will be first described separately on the Type 1 diabetes patients and on the Type 2 diabetes patients, and then on the pooled patients population.

LS means difference versus placebo at Week 24 will be provided, as well as the corresponding standard error (SE) and 95% CI, within each subgroup. The significance level of the treatment-by-subgroup factor interaction term at Week 24 will be also provided for each factor for descriptive purpose. Forest plots will be provided. For each subgroup analysis, subgroups will be included in

the analysis only if there are ≥ 10 patients by subgroup and treatment arm. Otherwise, unless specified below, the subgroups not meeting the required number of patients will be pooled to form larger subgroups if possible, or they will be excluded from analysis.

Subgroups of interest are:

- BMI: <25 , [25-30[, ≥ 30 kg/m²;
- Gender: Female, Male;
- Menopausal status, for female only: Yes, No;
 1. For post-menopausal women: type of hormone replacement therapy : estrogen only, estrogen and progesterone, no estrogen or progesterone;
- Race: White/Caucasian, non-White/Caucasian;
- Ethnicity: Hispanic, non-Hispanic, Not Reported/Unknown;
- Region: North America, Europe;
- Age: <65 , [65–75], >75 / <65 , ≥ 65 years old;
- Duration of diabetes : <5 , [5-10], >10 years if the number of patients by subgroup meets the requirement (see above); otherwise by tertiles;
- ASCVD as per protocol: Yes, No;
- ASCVD including TIA as per the 2013 AHA/ACC guideline (see [Section 2.1.1](#)): Yes, No;
- Background LMT:
 2. Any statin versus no statin at randomization
 3. no LMT (neither statin or other LMT), versus other LMT only (without statin), versus statin alone, versus any statin plus other LMT
 4. High intensity statin at randomization vs medium or low intensity statin at randomization
- Prior history of myocardial infarction (Silent or acute MI) or ischemic stroke: Yes, No;
- CKD: Yes, No (from cardiovascular medical history CRF page);
- Estimated GFR class: <30 , [30- 60[, [60-90[, ≥ 90 mL/min/1.73 m². If there are not enough patients with eGFR <30 , the <30 and the [30-60[categories will be pooled together;
- Baseline albumin/creatinine ratio: <30 , [30-300[, ≥ 300 mg/g (<3.39 , [3.39-33.9[, ≥ 33.9 mg/mmol);
- Diabetic kidney disease category as defined below ([Appendix C](#)) (1):
 1. Category 1 : G1A1, G2A1
 2. Category 2 : G1A2, G2A2, G3aA1
 3. Category 3 : G1A3, G2A3, G3aA2, G3bA1
 4. Category 4 : G3aA3, G3bA2, G3bA3, G4A1, G4A2
 5. Category 5 : G4A3, G5A1, G5A2, G5A3

If the numbers of patients by subgroup don't allow this subgroup analysis, other groupings will be explored.

- Baseline calculated LDL-C: <100, [100-130[, [130-160[, ≥ 160 (<2.59[, [2.59-3.37[, [3.37-4.14[, ≥ 4.14 mmol/L) if the number of patients by subgroup meets the requirement (see above). Otherwise one of the following groupings will be explored:
 1. <100[, [100-130[, ≥ 130 (<2.59[, [2.59-3.37[, ≥ 3.37 mmol/L)
 2. by tertiles
- For this specific subgroup factor, the MMRM model will include the same covariates than for other subgroup factors, except that the baseline calculated LDL-C value will be replaced by the baseline calculated LDL-C category. Therefore, the model for the overall population will include fixed categorical effects for treatment group, randomization strata (as per IVRS), baseline calculated LDL-C category, time point, and the interactions treatment-by-time point, strata-by time point, baseline calculated LDL-C category-by-time point, treatment group-by-baseline calculated LDL-C category, and treatment group-by-baseline calculated LDL-C category-by-time point. For assessing the treatment effect by diabetes type, the same model will be fitted within each stratum, therefore without the strata factor and the interaction strata-by time point.
- Baseline non-HDL-C: <130, [130-160[, [160-190[, ≥ 190 (<3.37, [3.37-4.14[, [4.14-4.91[, ≥ 4.91 mmol/L)) if the number of patients by subgroup meets the requirement (see above). Otherwise one of the following groupings will be explored:
 1. <130[, [130-160[, ≥ 160 (<3.37, [3.37-4.14[, ≥ 4.14 mmol/L)
 2. by tertiles (only if no sufficient patients in previous grouping)
- Baseline TGRL :
 1. <30 mg/dL, ≥ 30 mg/dL
 2. by quintiles if the number of patients by subgroup meets the requirement (cf. above); otherwise, by tertiles.
- Baseline HDL-C: low HDL-C (for men <40 mg/dL (<1.04 mmol/L) / for women <50 mg/dL (<1.29 mmol/L)), high HDL-C (for men ≥ 40 mg/dL (≥ 1.04 mmol/L) / for women ≥ 50 mg/dL (≥ 1.29 mmol/L));
- Baseline fasting TG:
 1. <150, [150-200[, ≥ 200 mg/dL (<1.7, [1.7-2.3[, ≥ 2.3 mmol/L) and
 2. <150, ≥ 150 mg/dL (<1.7, ≥ 1.7 mmol/L, mixed dyslipidaemia) and
 3. by quintiles if the number of patients by subgroup meets the requirement (see above); otherwise, by tertiles;
- Baseline Lp(a):
 1. <30, [30-50[, ≥ 50 mg/dL (<0.3, [0.3-0.5[, ≥ 0.5 g/L) and
 2. <30, ≥ 30 mg/dL ((<0.3, ≥ 0.3 g/L);
- Baseline total PCSK9 level: <median, \geq median ng/ml;
- Baseline free PCSK9 level: <median, \geq median ng/ml;
- Baseline HbA1C: <7, [7-9[, $\geq 9\%$ if the number of patients by subgroup meets the requirement (cf. above); otherwise: <median, \geq median and by tertiles;
- Controlled vs uncontrolled DM, based on baseline HbA1c: <7, $\geq 7\%$;

- Insulin daily dose per kg at baseline (only in type 2 DM patients): ≤ 1 U/kg/day, > 1 U/kg/day

2.4.5.2 Analyses of secondary lipid efficacy endpoints

2.4.5.2.1 Continuous endpoints anticipated to have a normal distribution

Continuous secondary variables defined in [Section 2.1.3.2](#) anticipated to have a normal distribution (eg, lipids other than TG, TGRL and Lp(a)) will be analyzed using the same MMRM model as for the primary endpoint. Specifically, the model for assessing the treatment effect in the pooled data will contain fixed categorical effects of treatment group, randomization strata (as per IVRS), planned time points to Week 24, treatment group-by-time point interaction, and strata-by-time point interaction, as well as, the continuous fixed covariates of corresponding baseline value and baseline value-by-time point interaction. The significance level (P-value) of the treatment-by-strata interaction term at Week 24 will be also provided for this model for descriptive purpose. In case of non-convergence of the model, a model with less interaction coefficients will be fitted. A forest plot will be provided for percent change in calculated LDL-C from baseline to week 24 on mITT population.

